# 9.2 Efficacy Evaluation

The evaluation will be started from Month 3. Hematologic ORR is defined as the sum of CR and PR.

Hematologic CR: Clinical symptoms and signs turn normal (splenomegaly disappears), and blood cell count completed turn normal, ie, hemoglobin >110 g/L, platelets >100 ×  $10^9$ /L, ANC >1.5 ×  $10^9$ /L, lymphocyte count <4 ×  $10^9$ /L, and LGLs in peripheral blood are within the normal range (<0.5 ×  $10^9$ /L).

Complete molecular response: No LGLs can be detected when reaching CR (negative TCR rearrangement by flow cytometry or polymerase chain reaction [PCR]).

Hematologic PR: Hematologic PR is defined as blood cell count that do not meet criteria for CR but improvement is observed, such as neutrophil counts  $>0.5 \times 10^9/L$  without repeated infection, an increase of hemoglobin level from baseline by more than 20 g/L without blood transfusion, platelets  $>50 \times 10^9/L$ .

SD: CR/PR criteria are not met after standardized treatment for 4 months, but no significant progression is observed.

PD: Cytopenia (hemoglobin decreased by 2 g/dL, <10 g/dL; ANC decreased by  $0.5 \times 10^9$ /L, <1.0 ×  $10^9$ /L; platelets decreased by  $20 \times 10^9$ /L, <100 ×  $10^9$ /L, requiring blood transfusion) or progressive worsening of organomegaly.

PFS: PFS is defined as the time from the first day of study to PD or death, including PD and death from any cause (eg, PD, toxicity, unrecorded progression in a new treatment, or death).

DoR: DoR is defined as the time when CR or PR is met until the first date of recurrent or progressive disease.

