## 5.2 Inclusion and Exclusion Criteria

#### 5.2.1 Inclusion Criteria

- 1. Patients who fulfill the diagnostic criteria for T-LGLL or CLPD-NK specified in the 2016 WHO Classification of Lymphoid Neoplasms [1]
- 2. Patients are fully informed about the study and willing to participate in the study and provide written ICF
- 3. Male or female, aged  $\geq$ 18 years
- 4. Treatment-naive patients, or patients treated with or relapsed from a non-methotrexate/ thalidomide-based regimen
- 5. Patients with at least one of the following indications for LGLL treatment:
  - a. ANC  $<0.5 \times 10^9$ /L, or neutropenia with recurrent infections
  - b. Hemoglobin <100 g/L, or requiring infusion of red blood cells
  - c. Platelets level  $< 50 \times 10^9 / L$
  - d. Concomitant autoimmune diseases requiring treatment
  - e. Symptomatic splenomegaly
  - f. Severe B symptoms (fever of unknown cause with body temperature over 38 °C; night sweats; weight loss of ≥10% within half a year)
  - g. Pulmonary hypertension
- 6. Patients with Eastern Cooperative Oncology Group (ECOG) score of 0 to 2 (Appendix 1)
- 7. Patients with life expectancy  $\geq 6$  months.

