## **6.3.2** Permitted Medications

The investigator may prescribe any concomitant medication or therapy deemed necessary to provide adequate supportive treatment throughout the study, including those listed below:

Standard supportive treatment (antiemetics, antidiarrheals, anticholinergics, spasmodic drugs, antipyretics, antihistamines, analgesics, and other medications designed to treat the symptoms or signs) will be administered as clinically indicated according to local standard of care and when deemed necessary by the investigator.

- Growth factor support, erythropoietin, and blood product transfusion are allowed for the treatment of symptoms or signs of neutropenia, anemia, or thrombocytopenia according to local standard of care.
- Infectious complications with documented evidence should be treated with oral or intravenous antibiotics, or other anti-infective drugs that the investigator considers appropriate for the infectious condition according to local standards

of care. If clinically indicated, the investigator may administer prophylactic anti-infective therapy to patients according to local standards of care.

- Prevention of tumor lysis syndrome (TLS): For patients with elevated risk of TLS such as high tumor load and renal impairment, adequate hydration and alkalinization should be performed during treatment according to clinical practice, and blood chemistry should be closely monitored.
- Prevention and treatment of HBV activation.
- Other medications for concomitant diseases: Treatment for hypertension, diabetes, etc.
- If a patient experiences an AE during study treatment, the investigator should provide appropriate treatment according to clinical practice, including but not limited to antiemetics, hepatoprotective drugs, drugs for increasing leukocyte, transfusion/blood products, anti-infection drugs, and drugs causing QTc prolongation.

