# 7.4 Guidelines for Dose Adjustment and Discontinuation

In the event of toxicity, the investigator should accurately assess the severity of AEs and serious adverse events (SAEs) based on the patient's condition and the National Cancer Institute (NCI) Common Terminology Criteria for Adverse Events (CTCAE, Version 5.0). Appropriate medication (including infusions, cytokine growth factors, antiemetics, antidiarrheals, etc.) should be administered to treatment AEs. All AEs will be assessed from the time of the first dose of the study treatment until the final study visit. Patients who have experienced AEs may be followed up after the EOS visit for additional assessments until the AE resolves or is deemed stable.

For patients who are unable to tolerate the protocol-specified administration regimen, treatment discontinuation or dose adjustments are allowed. Before treatment discontinuation and dose adjustment, the attribution of AEs to the 3 drugs (thalidomide, methotrexate, and prednisone) should be determined. For non-hematological toxicities attributable to methotrexate and prednisone (not thalidomide), administration of thalidomide may be continued.

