# 9.3 Study Endpoints Definition and Evaluation

## **Primary Endpoint:**

• CRR of patients with symptomatic LGLL treated with thalidomide, prednisone, and methotrexate.

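### The CR definition behind the primary endpoint does not require the blood counts to be free of transfusion, erythropoietin or growth-factor support

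*Supplement*

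**What the plan says.** The primary endpoint (section 9.3) is "CRR of patients with symptomatic LGLL treated with thalidomide, prednisone, and methotrexate". Section 9.2 defines CR: "Hematologic CR: Clinical symptoms and signs turn normal (splenomegaly disappears), and blood cell count completed turn normal, ie, hemoglobin >110 g/L", then platelets above 100, ANC above 1.5 and lymphocytes below 4 (all × 10⁹/L), "and LGLs in peripheral blood are within the normal range" (below 0.5 × 10⁹/L). All of these must hold together. The definition contains no support-free interval and no confirmation requirement.

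The PR definition in the same section gives as one of its examples "an increase of hemoglobin level from baseline by more than 20 g/L without blood transfusion". It has no growth-factor condition.

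Section 6.3.2 states: "Growth factor support, erythropoietin, and blood product transfusion are allowed for the treatment of symptoms or signs of neutropenia, anemia, or thrombocytopenia". For adverse events it also lists "drugs for increasing leukocyte, transfusion/blood products". Section 7.4 on toxicity adds "Appropriate medication (including infusions, cytokine growth factors, antiemetics, antidiarrheals, etc". None of these passages refers to the timing of response assessment. Section 5.2.1 admits patients on the criterion "Hemoglobin <100 g/L, or requiring infusion of red blood cells", so some patients will enter the trial already on transfusion.

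**The concern.** Transfusion, erythropoietin and growth factors act on hemoglobin, platelets and neutrophils, which are three components of the CR definition. If a count obtained under support may be used, part of the primary endpoint can reflect supportive care and not the study regimen. The study has one treated group, its CRR is set against a historical 47%, and no central response review is described. The possible error runs in one direction, towards more CRs. The authors evidently had transfusion in mind when writing the PR hemoglobin example, which makes its absence from CR stand out.

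**Working it through.** **1. Is the condition supplied elsewhere?** Sections 9.2, 9.3, 6.3.1 to 6.3.3, 7.4, the visit lists in 8.2 and the analysis sections 11.1 to 11.3 of version 2.0 contain no support-free condition for CR. Section 11.3 leaves only the rules for DoR, PFS and OS to the SAP. CR is defined in the protocol, so this is not a detail deferred to the SAP.

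**2. Who can be misclassified?** CR is a conjunction. A supported hemoglobin satisfies the hemoglobin component only. A patient is wrongly scored as CR only if symptoms and signs, spleen, lymphocytes, LGLs and the remaining counts all qualify, and the residual cytopenia is lifted over its threshold by support.

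**3. The plan's own sample size.** From section 4.5: p0 = 0.47, p1 = 0.70, two-sided α = 0.05, power 80%.

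n = [1.960·√(0.47·0.53) + 0.842·√(0.70·0.30)]² / (0.70 − 0.47)² = (0.978 + 0.386)² / 0.0529 = 35.2

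This agrees with the stated 35. The point does not alter this number.

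**4. A success cutoff.** The plan states none, so I derive one from the exact 95% CI that section 11.3 prescribes. With n = 35 and p = 0.47:

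- P(X ≥ 22) = 0.0435, above 0.025, so the interval for 22/35 still includes 47%.
- P(X ≥ 23) = 0.0200, below 0.025. The interval for 23/35 is 47.8% to 80.9%.

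The cutoff is therefore 23 of 35.

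**5. Effect of misclassification.** Let m be the share of true non-CR patients scored as CR because of support. The documents give no value, so m is an assumption, taken over 0% to 20%. With a true support-free CRR of 47%:

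apparent CRR = 0.47 + 0.53·m

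| m | Expected patients affected (35 × 0.53 × m) | Apparent CRR | P(X ≥ 23), n = 35 |
|---|---|---|---|
| 0% | 0 | 47.0% | 2.0% |
| 5% | 0.9 | 49.7% | 4.1% |
| 10% | 1.9 | 52.3% | 7.7% |
| 20% | 3.7 | 57.6% | 21.3% |

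If all 42 enrolled patients were analyzed, the same derivation gives a cutoff of 27, and the chances are 1.8%, 4.0%, 8.0% and 23.7%.

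**6. Effect on the estimate.** If the apparent CRR were 70%, the support-free CRR would be (0.70 − m)/(1 − m): 68.4% at m = 5%, 66.7% at 10% and 62.5% at 20%.

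**The case against.** - *Normal LGLs, lymphocytes, spleen and symptoms are also needed.* This is correct and it limits the point. A reader might infer that a neutrophil count raised by a growth factor, or a hemoglobin raised by transfusion, is enough for CR. The definition does not support that, because each supported count meets only its own component.
- *Normal symptoms and signs could be taken to exclude a patient who still needs support.* Section 6.3.2 allows support for symptoms or signs of cytopenia, and transfusion need is itself an entry indication, so this is a fair reading. But it is implicit, and the explicit wording in PR weakens it. Two assessors could score the same patient differently. The amendment summary for version 2.0 gives that kind of disagreement as the reason for unifying the PD criteria.
- *The contrast with PR is narrow.* This stands. The transfusion clause covers hemoglobin only and sits in a list of examples, and PR is silent on growth factors. It would go too far to say that CR is easier to reach than PR in general.
- *The bias against 47% is not established.* This stands in part. The CR definition used in the historical cyclophosphamide series is not in the documents. If that series also counted supported patients, the bias in the comparison would be smaller or absent. The upward effect on this trial's own CRR remains.
- *Growth factors for neutrophils are not named as a specific drug.* The wording of 6.3.2 covers them.

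**Conclusion.** The point holds as a gap in the definition of the primary endpoint: applied literally, section 9.2 can score as CR a patient whose only remaining cytopenia is masked by permitted support. The effect on the trial's CRR can only be upward. Its size is unknown. Under the assumed range of 0% to 20% of non-CR patients misclassified, the chance of reaching 23 of 35 at a true CRR of 47% runs from 2.0% to 21.3%. The upper end needs about one in five non-CR patients to meet every other criterion while masked by support, and nothing in the documents says this is likely. A reader might infer that the false-positive rate is in fact inflated by a known amount; the documents do not support that. The figures rest on the derived cutoff, on n = 35 evaluable patients, and on the labelled assumption about m.

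**What to change.** Add to section 9.2 that counts used for CR and PR must be obtained without red-cell or platelet transfusion, erythropoietin or growth factors during an interval before the sample. The sponsor should fix that interval in advance; it may differ by type of support. State that a visit that does not meet this condition is not scored as CR. Record the dates of transfusion and growth-factor use on the CRF. Section 6.3.1 already has the investigator ask about new medication at each visit, but the visit lists in 8.2 contain no dated log of this support, so a small CRF addition is probably needed.

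This changes only how response is scored. It restricts no patient's supportive care and leaves the planned sample size as it is. The costs are the added wording, the CRF field and possibly a slightly lower CRR.

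### PR and PD in Section 9.2 are not matched to the entry criteria, so ORR may be inflated and neutrophil progression missed or dated late

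*Supplement*

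**What the plan says.** All counts below are × 10⁹/L unless another unit is given. The text reviewed is protocol version 2.0.

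- **Entry (Section 5.2.1, item 5).** The rule is "Patients with at least one of the following indications for LGLL treatment", and there are seven. Item a is ANC below 0.5, "or neutropenia with recurrent infections". Items b and c are hemoglobin below 100 g/L (or red cell transfusion need) and platelets below 50. Items d to g are not blood counts; item d, for example, is "Concomitant autoimmune diseases requiring treatment".
- **PR (Section 9.2).** "Hematologic PR is defined as blood cell count that do not meet criteria for CR but improvement is observed, such as neutrophil counts" above 0.5, continuing "without repeated infection, an increase of hemoglobin level from baseline by more than 20 g/L without blood transfusion, platelets" above 50. Hemoglobin is a change from baseline; the other two are levels. Nothing says whether the three are alternatives or joint conditions, or which applies to which patient.
- **PD (Section 9.2).** "PD: Cytopenia (hemoglobin decreased by 2 g/dL, <10 g/dL; ANC decreased by" 0.5 and to below 1.0; platelets down by 20 and to below 100; then "requiring blood transfusion) or progressive worsening of organomegaly". No reference value is given for any of the falls. It is also unclear whether the transfusion clause covers platelets only or every lineage.
- **Endpoints.** ORR, PR rate, PFS and DoR are secondary (Section 9.3). "PFS is defined as the time from the first day of study to PD or death, including PD and death from any cause". DoR ends at recurrent or progressive disease, and recurrence is not defined.
- **Use of PD.** PD is also a withdrawal criterion (Section 5.3, item 2).

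**The concern.** A response limit should describe a change in what was abnormal. Here the neutrophil and platelet limits sit at the entry cut-offs, but one indication out of seven is enough to enter. Patients who qualify by another route may be above both limits before the first dose. For them, only the word improvement separates PR from no response, and for neutrophils and platelets it has no size and no lineage. For indications d to g, PR is judged on counts that may never have been the problem.

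PD has the opposite difficulty. A fixed fall of 0.5 is large compared with the neutrophil counts of patients entered on ANC below 0.5, and in the lowest range there is no room for it. The amendment summary gives more uniform judgment between doctors as the reason for the current PD criteria. That aim is not met if the neutrophil limb cannot operate in many patients of the first-listed entry group.

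At stake are four secondary endpoints: ORR and PR rate through the first problem, PFS and DoR through the second.

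**Working it through.** **The only planning figure.** Section 4.5 gives 35 evaluable patients for the CRR test (47% against 70%, two-sided 0.05, 80% power). The one-sample normal approximation gives

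n = (1.960·√(0.47·0.53) + 0.842·√(0.70·0.30))² / 0.23² = 35.16,

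so 36 after rounding up, in line with 35. No size is planned for ORR or PFS; I use 35 only as a denominator.

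**PR against entry**

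1. Entered on hemoglobin below 100 g/L, with (for illustration) ANC 2.0 and platelets 150: both absolute limits are exceeded on day 0. With no hemoglobin response, a small rise in ANC or platelets, short of CR, can be read as PR.
2. Entered only on indications d to g: the same, and no PR criterion addresses the reason for entry.
3. Entered on ANC 0.45, later 0.51 and free of repeated infection: a rise of 0.06 crosses the limit and is PR.
4. Entered on ANC below 0.5 or on platelets below 50: the patient's own limit is not met at baseline, but the other lineage's limit may be.

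**Size for ORR.** One misclassified patient moves ORR by 1/35 = 2.9 points. The number misclassified cannot be derived from the documents. As an assumption only, take a true ORR of 72% (the historical control's effective rate) and let a share f of true non-responders be called PR. Then observed ORR = 0.72 + 0.28·f:

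| f | observed ORR |
|---|---|
| 0 | 72.0% |
| 10% | 74.8% |
| 25% | 79.0% |
| 50% | 86.0% |

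**Neutrophil limb of PD.** The count must reach the reference value minus 0.5 or lower, and be below 1.0.

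| Reference ANC | Reference − 0.5 | Can it be met? |
|---|---|---|
| 0.49 | −0.01 | no |
| 0.50 | 0.00 | only at zero |
| 0.60 | 0.10 | yes, but 0.6 to 0.2 is a fall of 0.4 and does not count |
| 0.80 | 0.30 | yes |
| 1.00 | 0.50 | yes |

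If ANC never reaches 0.5, entry, best and last values are all below 0.5, so no choice of reference makes the limb attainable. If the best value P lies between 0.5 and 1.0, counts above P − 0.5 but below 0.5 are back under the entry cut-off and still not PD. From P of 1.0 upward, a return below 0.5 is always a fall of more than 0.5, and the gap closes.

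**Other limbs.** Platelet PD cannot be met from a reference below 20 (19 − 20 = −1). From 20 to 49 it requires a fall to between 0 and 29. Hemoglobin PD is attainable from entry values (9.9 to 7.9 g/dL).

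**The case against.** - **PR also requires improvement.** This stands: a patient with unchanged counts is not PR on the text. A reader might infer that ORR is overstated by construction, and the wording does not support that. What remains is that improvement has no size or lineage for ANC and platelets. The infection condition narrows the neutrophil example but does not remove it.
- **PD has other routes.** This stands: hemoglobin, platelets, organomegaly and death remain PFS events. Entry under the second half of item 5a sets no ANC ceiling, so the neutrophil limb can work there (0.8 to 0.3). It would be wrong to infer that PFS is overstated by construction or that the whole first-listed group is unprotected.
- **Persistent neutropenia is non-response.** This also stands: it fits SD, and lack of clinical benefit has its own withdrawal rule. The gap concerns worsening and loss of response.
- **A fall from 1.2 to 0.6 looks like PD and PR at once.** A reader might infer a contradiction. If 1.2 is the baseline, there is no improvement and so no PR. If it is an on-study peak, this is PR followed by PD, an ordinary sequence.
- **The SAP may settle this.** Section 11.3 leaves the rules for DoR, PFS and OS analyses to an SAP that is not shown, so a missing reference value alone would be weak ground. But Section 11.3 does not defer the response criteria, which Section 9.2 sets, and no reference value repairs the neutrophil limb for patients who stay below 0.5.
- **Impact is limited.** CRR is primary and uses neither rule; ORR is estimated with an exact interval, and PFS and DoR are summarized descriptively.

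**Conclusion.** The point holds as a defect in the secondary-endpoint definitions that should be corrected. Followed as written, the PR limits allow a patient who entered for another reason to be counted as a responder on a trivial rise, so ORR and the PR rate may be inflated. Each such patient adds 2.9 points at n = 35. The total depends on the mix of indications and on how strictly assessors read improvement, neither of which the documents give; it is zero if improvement in the affected lineage is enforced in practice.

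The neutrophil limb of PD cannot be met from an entry ANC below 0.5 and misses loss of a low-level response, so PFS and DoR may record neutrophil progression late or not at all. The effect on their medians cannot be computed. The documents support a risk of bias in a favorable direction, not a certain overstatement, and CRR is not affected.

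**What to change.** In Section 9.2, for the ORR analysis:

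1. Judge PR only on the lineage or lineages that met an entry indication at baseline, with no worsening in the others. Because this alone leaves 0.45 to 0.51 as PR, state also what size of rise in ANC and platelets counts as improvement.
2. For patients entered only on indications d to g, either state a PR criterion or count them as responders only if they reach CR. Keep them in the denominator under both options, since dropping them would change the population to which ORR refers.

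For PFS and DoR:

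3. State the reference value for each fall in the PD rule and which lineages the transfusion clause covers.
4. Reconcile the neutrophil limb with the entry and PR limits, so that loss of response in patients neutropenic at entry can count as an event. Measuring from the best on-study value does not achieve this if that value stays below 0.5. Say whether such a loss is recurrence for DoR.

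PD also triggers withdrawal, so the sponsor must reconcile Sections 5.2.1, 5.3 and 9.2; no threshold should be taken from this review.

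The cost is wording. Hematology is already collected after Cycle 1 and every 3 months thereafter (Section 8.3). The downside is that ORR and PFS may look slightly less favorable.

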# 9.3 Study Endpoints Definition and Evaluation

## **Primary Endpoint:**

• CRR of patients with symptomatic LGLL treated with thalidomide, prednisone, and methotrexate.

## **Secondary Endpoints**

### 1. Secondary Safety Endpoint

Incidence and severity of hematological and non-hematological AEs

Safety endpoints include SAEs, treatment-emergent adverse events (TEAEs), physical examination (including ECOG performance status), vital sign measurements, standard clinical laboratory parameters, and ECG. TEAEs will be graded according to NCI CTCAE Version 5.0.

# 2. Secondary Efficacy Endpoints

• Response rates: ORR and PR rate (time frame: 24 months after the last treatment)

Point estimates of rates will be calculated for each protocol analysis set. An estimate of the 95% CI for the response rate will also be derived. Graphical and descriptive analyses will be used to explore associations between relevant markers and responses.

• PFS and OS (time frame: 24 months after the last treatment)

Time from the first day to PD or death from any reason. The median duration of the overall response will be assessed with a 95% CI.

• DoR (time frame: 24 months after the last treatment)

The time when CR or PR is met until the first date of recurrent or progressive disease. The median duration of the overall response will be assessed with a 95% CI.

• Effect of biomarkers on efficacy and adverse reactions

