## 4.4 Follow-up

Patients who withdraw from the study due to intolerable AEs will be followed up in this study until the events resolve to Grade 1 or lower, or the AE is stable. Patients will be followed up for up to 24 months after completion of the treatment, or until study termination, PD, initiation of new anti-tumor therapy, or death.

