## 4.8 Study Termination

EOS is defined as the last patient last visit at the end of the follow-up period, which will be the last data collection point and the last patient may be an outpatient or laboratory sample. EOS is expected to occur approximately 2 years after enrollment of the last patient. A patient will be considered to have completed the study if he/she dies or meets any of the withdrawal criteria.

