# **8.4** Early Withdrawal (Discontinuation of Study Treatment)

### Three months after the Last Treatment:

- Physical examinations
- Vital signs measurements (body temperature, pulse, systolic and diastolic blood pressure, and respiratory rate)
- ECOG performance status
- Disease-related signs and symptoms
- Assessment and recording of AEs
- Hematology: Hemoglobin, ANC, WBC count, platelets
- Blood chemistry: Serum glucose, AST, ALT, total bilirubin, creatinine, Na, K, uric acid, total protein, and albumin
- Serum LDH
- Serum immunoglobulin quantification
- Urinalysis and stool
- Detection of LGLs in peripheral blood
- Detection of peripheral blood lymphocyte subsets (B/T/NK; Treg; T-cell immune function; TH1/TH2)
- Peripheral blood flow cytometry
- Peripheral blood TCRvβ flow cytometry
- Bone marrow smear, bone marrow biopsy, and immunohistochemistry
- Chromosome karyotype examination in bone marrow or peripheral blood
- ECG
- Evaluation of measurable lesions (including neck, chest, abdomen, and pelvis) by CT in patients with lymph node enlargement before admission
- Assessment of cardiac function and ejection fraction by two-dimensional echocardiography; abdominal color Doppler ultrasound, etc.
- Coagulation function

Following this assessment, patients will be followed up twice a year until the EOS, including survival, disease status, and long-term toxicity.

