# 11.3 Efficacy Analysis

The efficacy analysis will involve CRR and ORR (sum of CR and PR rates). Efficacy variables will be tabulated and summarized. For the numbers and percentages of CRR

and ORR, point estimates and 95% exact binomial CIs will be provided.

Time-to-event variables including DoR, PFS, and OS will be summarized descriptively using the Kaplan-Meier method. The rules for DoR, PFS, and OS analyses will be specified in the Statistical Analysis Plan (SAP). Growth modulation indices (intrasubject ratios of DOR, PFS, and OS, post-study treatment versus DOR, PFS, and OS post the most recent prior treatment regimen) will be summarized.

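### OS is given the same definition as PFS, the follow-up sections conflict on whether survival is collected after progression, the OS growth modulation ratio cannot exceed 1, and DoR leaves death in remission unaddressed

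*Supplement*

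**What the plan says.** All references are to protocol version 2.0.

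- **OS and PFS.** Section 9.3 has one bullet, "PFS and OS (time frame: 24 months after the last treatment"), followed by one definition for both endpoints: "Time from the first day to PD or death from any reason". The synopsis repeats it. Section 9.2 says "PFS is defined as the time from the first day of study to PD or death" and has no entry for OS.
- **DoR.** Section 9.2: "DoR is defined as the time when CR or PR is met until the first date of recurrent or progressive disease". Section 9.3 agrees. Neither names death.
- **Follow-up that stops at progression.** Section 4.4 follows patients for up to 24 months after treatment, or "until study termination, PD, initiation of new anti-tumor therapy, or death". Section 5.3 lists PD as a withdrawal criterion, and Section 4.8 adds: "A patient will be considered to have completed the study if he/she dies or meets any of the withdrawal criteria".
- **Follow-up that does not stop at progression.** Section 8.4, on early discontinuation: "patients will be followed up twice a year until the EOS, including survival, disease status, and long-term toxicity". Section 8.5.1 sets six-monthly survival follow-up for 2 years from the end of treatment, with no stop at PD.
- **Growth modulation index.** Section 11.3 and the synopsis plan within-patient "ratios of DOR, PFS, and OS, post-study treatment versus DOR, PFS, and OS" after the most recent prior regimen.
- **Deferral.** Section 11.3 leaves the analysis rules for DoR, PFS and OS to an SAP that is not among the documents.

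**The concern.** A report that follows the text would print the same curve twice, once labelled PFS and once OS. If the statistician instead takes OS to mean death, the data may not support it, because a site working from Section 4.4 or 4.8 can close a patient's record at progression. The amendment summary suggests that this matters in practice: its reason for dropping TTNT is that patients are withdrawn at progression and some are then lost. OS needs contact after that same point and was kept.

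The OS ratio would be read as a comparison with the patient's previous treatment, which it cannot be. For DoR, PFS counts death and DoR is silent, so two analysts could treat a death in remission differently and both claim to follow the protocol.

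**Working it through.** The plan states no figure on this point, so there is none to reproduce. The first three steps compare text or use algebra; the fourth is an illustration.

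**1. Definitions**

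| Endpoint | Start | Event | Source |
|---|---|---|---|
| PFS | first day of study | PD or death | 9.2 |
| PFS and OS | first day | PD or death | 9.3, synopsis |
| OS alone | none given | none given | not in 9.2 or 9.3 |
| DoR | CR or PR met | recurrence or PD | 9.2, 9.3 |

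Reading the shared sentence as PD for PFS and death for OS does not work, because Section 9.2 already counts death as a PFS event.

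**2. Follow-up**

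For a patient who progresses, Section 4.4 ends follow-up and Sections 4.8 and 5.3 make the patient a completer. Sections 8.4 and 8.5.1 keep the patient under survival follow-up. Section 4.8 also expects the end of study about 2 years after the last enrolment, whereas thalidomide for up to 2 years (Section 4.2) plus 2 years of survival follow-up (Section 8.5.1) gives 2 + 2 = 4 years for a patient enrolled last.

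**3. OS ratio**

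Let *a* > 0 be the time from the prior regimen to study entry and *b* the survival on study. Survival counted from the prior regimen is *a* + *b*, so the ratio is *b*/(*a* + *b*) < 1 for every patient. It rises with *b* but cannot reach 1, and it depends on *a*, which the study treatment does not affect. If the denominator stopped at study entry, it would be the gap between regimens, with no death possible. If OS kept its written definition, the ratio would repeat the PFS ratio.

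**4. Size (illustrative)**

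Inputs: Section 2.2 gives a median survival above 10 years for most LGLL patients; exactly 10 is used, so the death hazard is h_d = ln 2/10 = 0.0693 per year. The documents give no time to progression, so medians of 1.5 to 8 years are assumed, with h_p = ln 2/median. N = 42 (Section 4.5). Hazards are constant and the horizon is 4 years.

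- OS, death only: exp(−4h_d) = exp(−0.277) = 75.8%, if progression does not change the death hazard.
- OS as written: exp(−4(h_p + h_d)). For a 3-year median, exp(−4 × 0.3004) = 30.1%.
- Expected deaths: 42 × (1 − 0.758) = 10.2. Deaths seen if follow-up stops at PD: 42 × h_d/(h_p + h_d) × (1 − exp(−4(h_p + h_d))). For 3 years, 42 × 0.231 × 0.699 = 6.8.
- True OS if the death hazard after PD is *k* times higher: exp(−4(h_p + h_d)) + h_p/(h_p + h_d − k·h_d) × [exp(−4k·h_d) − exp(−4(h_p + h_d))]. For 3 years and k = 2, 0.3008 + 1.429 × (0.5743 − 0.3008) = 69.2%.

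| Assumed median time to PD (years) | 4-year OS as written | Median as written (years) | Deaths seen of 10.2 | True 4-year OS, k = 1 / 2 / 3 |
|---|---|---|---|---|
| 1.5 | 11.9% | 1.30 | 4.8 | 75.8 / 65.5 / 57.1% |
| 3 | 30.1% | 2.31 | 6.8 | 75.8 / 69.2 / 63.6% |
| 5 | 43.5% | 3.33 | 7.9 | 75.8 / 71.4 / 67.6% |
| 8 | 53.6% | 4.44 | 8.7 | 75.8 / 72.9 / 70.5% |

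The deaths-seen column takes k = 1. Kaplan-Meier with censoring at PD estimates 75.8% in every row: no bias at k = 1, and an overstatement of 75.8 − 72.9 = 2.9 to 75.8 − 57.1 = 18.7 points for k of 2 to 3.

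For DoR, with the same hazards counted from response, the median is 1.5, 3, 5 or 8 years with deaths censored, and 1.30, 2.31, 3.33 or 4.44 years with death as an event.

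**The case against.** The best defence is that Section 4.4 is the general efficacy rule and Section 8.5.1 the specific survival rule. Section 5.4 ties efficacy follow-up to PD or new therapy, and Section 4.2 describes the follow-up period as safety and efficacy. On that reading survival is collected, OS needs one sentence of definition, and the SAP may settle how death counts in DoR. The endpoints are secondary and summarised descriptively.

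Much of this stands. A reader might infer that follow-up ends at progression; the documents do not support that as a fact, because Sections 8.4 and 8.5.1 say otherwise. A reader might also infer that OS and DoR cannot be estimated. That goes too far: OS can be estimated once defined, if survival is collected, and DoR with deaths censored or treated as a competing event is estimable, though it answers a different question. The absence of an SAP from the documents is not a fault.

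The defence does not save the shared definition. An SAP can set censoring rules, but it should not quietly overrule a protocol endpoint, and it cannot recover deaths that sites did not record. Nor can it make the OS ratio exceed 1. That treatment-naive patients have no prior regimen is not a separate fault; it only means the index should be labelled as applying to previously treated patients.

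**Conclusion.** The point holds in a limited form. Two parts need no assumptions: OS as written is PFS, and the OS ratio lies below 1 whatever the treatment does. The follow-up rules contradict each other and must be reconciled. DoR needs a clarification.

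The size depends on rates the documents do not give. It would be tempting to quote a single figure: if 4 of 12 progressing patients died within 2 years, 4/42 = 9.5 points of OS would seem to be lost. The documents do not support that scenario. A 10-year median with constant hazard implies 1 − exp(−2 × 0.0693) = 12.9% dead at 2 years, or 12 × 0.129 = 1.55 of 12, and censoring at progression is unbiased unless the death hazard rises afterwards. The documents also give no ground for removing DoR from the index.

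The primary endpoint and the sample size are unaffected. The plan should be corrected, but this does not threaten its main conclusion.

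**What to change.** - **Sections 9.2, 9.3 and synopsis:** define OS separately as the first day of study to death from any cause, censored at the last date known alive. Keep the PD-or-death sentence for PFS alone.
- **Sections 4.4, 4.8, 8.4 and 8.5.1:** reconcile them so that PD, new therapy or withdrawal from treatment may end response assessment, while survival status is still collected on the schedule in Sections 8.4 and 8.5.1 unless consent is withdrawn. Give one end point for that schedule, since Section 8.4 runs to the end of study and Section 8.5.1 to 2 years after treatment, and align the end-of-study timing in Section 4.8 with it.
- **DoR:** state that death from any cause is an event, or that it is censored or a competing event.
- **Section 11.3 and synopsis:** delete OS from the growth modulation index and report the index only for previously treated patients.

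The cost is amendment wording and survival contacts after progression that Sections 8.4 and 8.5.1 already plan. Those contacts take some effort, since the sponsor reports losing some patients after withdrawal, and a longer end-of-study date may follow.
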